7.5 Assessing and Recording Adverse Events

An adverse event is defined as any untoward medical occurrence in a patient or clinical investigation subject administered a pharmaceutical product and which does not necessarily have to have a causal relationship with this treatment. An adverse event can therefore be any unfavorable and unintended sign (including an abnormal laboratory finding, for example), symptom, or disease temporally associated with the use of a medicinal product or protocol-specified procedure, whether or not considered related to the medicinal product or protocol-specified procedure. Any worsening (i.e., any clinically significant adverse change in frequency and/or intensity) of a preexisting condition that is temporally associated with the use of the Merck's and/or BIPi product, is also an adverse event.

Changes resulting from normal growth and development that do not vary significantly in frequency or severity from expected levels are not to be considered adverse events. Examples of this may include, but are not limited to, teething, typical crying in infants and children and onset of menses or menopause occurring at a physiologically appropriate time.

Merck product includes any pharmaceutical product, biological product, device, diagnostic agent or protocol-specified procedure, whether investigational (including placebo or active comparator medication) or marketed, manufactured by, licensed by, provided by or distributed by Merck for human use.

Adverse events may occur during the course of the use of Merck product in clinical trials or prescribed in clinical practice, from overdose (whether accidental or intentional), from abuse and from withdrawal.

Progression of the cancer under study is not considered an adverse event.

All adverse events that occur after the consent form is signed but before treatment allocation must be reported by the investigator if they cause the subject to be excluded from the trial, or are the result of a protocol-specified intervention, including washout or discontinuation of usual therapy, diet, placebo treatment or a procedure.

From the time of treatment allocation through 30 days following cessation of treatment, all adverse events must be reported by the investigator. Such events will be recorded at each examination on the Adverse Event case report forms/worksheets. The reporting timeframe for adverse events meeting any serious criteria is described in section 7.5. The investigator will make every attempt to follow all subjects with non-serious adverse events for outcome.

Adverse events will not be collected for subjects during the pre-screening period (for determination of archival tissue status) as long as that subject has not undergone any protocol-specified procedure or intervention. If the subject requires a blood draw, fresh tumor biopsy etc., the subject is first required to provide consent to the main study and AEs will be captured according to guidelines for standard AE reporting.

All adverse events, serious and non-serious, will be collected, documented and reported to the

company supporter by the investigator on the appropriate CRFs / SAE reporting forms (BI and Merck SAE report form).

For each adverse event, the investigator will provide the onset date, end date, CTC AE grade, treatment required, outcome, seriousness, and action taken with the investigational drug. The investigator will determine the relationship of the investigational drug to all AEs as defined below.

Adverse events with onset within first administration of afatinib therapy and 28 days after last administration of afatinib will be considered as on treatment. All AEs, including those persisting after end of study treatment must be followed up until they have resolved or have been sufficiently characterized or the principal investigator decides to not further pursue them. Serious and non-serious adverse events occurring later than 28 days after last administration of trial drugs will only be reported in case they are considered drug-related or trial (procedure) related.

7.5.1 Definition of an Overdose for This Protocol and Reporting of Overdose to Merck

For purposes of this trial, an overdose of pembrolizumab will be defined as any dose of 1,000 mg or greater (>5 times the indicated dose). No specific information is available on the treatment of overdose of MK-3475. Appropriate supportive treatment should be provided if clinically indicated. In the event of overdose, the subject should be observed closely for signs of toxicity.

If an adverse event(s) is associated with (“results from”) the overdose of a Merck product, the adverse event(s) is reported as a serious adverse event, even if no other seriousness criteria are met.

If a dose of Merck’s product meeting the protocol definition of overdose is taken without any associated clinical symptoms or abnormal laboratory results, the overdose is reported as a non-serious Event of Clinical Interest (ECI), using the terminology “accidental or intentional overdose without adverse effect.”

All reports of overdose with and without an adverse event must be reported within 24 hours to the company supporter and within 2 working days hours to Merck Global Safety. (Attn: Worldwide Product Safety; [contact])

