5.3 Definition of Dose Limiting Toxicities (DLT)

All toxicities will be graded using National Cancer Institute (NCI) CTCAE Version 4.0. The occurrence of any of the following toxicities during Cycle 1 will be considered a DLT, if judged by the Investigator to be possibly, probably or definitely related to study drug (either afatinib or MK-3475) administration:

1. Grade 4 non-hematologic toxicity (not laboratory).
2. Grade 4 hematologic toxicity lasting ≥ 14 days.
3. Grade 3 non-hematologic toxicity (not laboratory) lasting > 3 days despite optimal supportive care with maximal supportive care for diarrhea and rash. See description of maximal supportive care for diarrhea and rash attributed to afatinib below.
4. Any Grade 3 or Grade 4 non-hematologic laboratory value if:
 - Medical intervention is required to treat the patient, or
 - The abnormality leads to hospitalization, or
 - The abnormality persists as \geq grade 3 for > 1 week.
5. Febrile neutropenia Grade 3 or Grade 4:
 - Grade 3 is defined as ANC $< 1000/\text{mm}^3$ with a single temperature of > 38.3 degrees C (101 degrees F) or a sustained temperature of ≥ 38 degrees C (100.4 degrees F) for more than one hour
 - Grade 4 is defined as ANC $< 1000/\text{mm}^3$ with a single temperature of > 38.3 degrees C (101 degrees F) or a sustained temperature of ≥ 38 degrees C (100.4 degrees F) for more than one hour, with life-threatening consequences and urgent intervention indicated.
6. Thrombocytopenia $< 25,000/\text{mm}^3$ if associated with:
 - A bleeding event which does not result in hemodynamic instability but requires an elective platelet transfusion, or
 - A life-threatening bleeding event which results in urgent intervention and admission to an Intensive Care Unit
 - Grade 5 toxicity (i.e. death).
7. Diarrhea is an expected adverse event from afatinib. Diarrhea attributed to afatinib will be considered a DLT if grade 3 despite maximal medical management for > 72 hours. Maximal medical management will be defined as anti-diarrheal management that includes: loperamide, diphenoxylate and atropine, and tincture of opium. Grade 4 diarrhea will be considered a DLT.

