5.8 Subject Withdrawal/Discontinuation Criteria

Subjects may withdraw consent at any time for any reason or be dropped from the trial at the discretion of the investigator should any untoward effect occur. In addition, a subject may be withdrawn by the investigator or the company supporter if enrollment into the trial is inappropriate, the trial plan is violated, or for administrative and/or other safety reasons. Specific details regarding discontinuation or withdrawal are provided in Section 7.1.4 – Other Procedures.

A subject must be discontinued from the trial for any of the following reasons:

- The subject or legal representative (such as a parent or legal guardian) withdraws consent.
- Confirmed radiographic disease progression by RECIST 1.1

Note: A subject may be granted an exception to continue on treatment with confirmed radiographic progression if clinically stable or clinically improved by the primary investigator in consultation with the sponsor.

- Unacceptable adverse experiences as described in Section 5.2.1.2
- Intercurrent illness that prevents further administration of treatment
- Investigator's decision to withdraw the subject
- The subject has a confirmed positive serum pregnancy test
- Noncompliance with trial treatment or procedure requirements
- The subject is lost to follow-up
- Completed 24 months of uninterrupted treatment with MK-3475 or 35 administrations of study medication, whichever is later

Note: 24 months of study medication is calculated from the date of first dose.

- Administrative reasons

The End of Treatment and Follow-up visit procedures are listed in Section 6 (Protocol Flow Chart) and Section 7.1.5 (Visit Requirements). After the end of treatment, each subject will be followed for 30 days for adverse event monitoring. Subjects who discontinue for reasons other than progressive disease will have post-treatment follow-up for disease status until disease progression, initiating a non-study cancer treatment, withdrawing consent or becoming lost to follow-up.

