2. In general, the window for each visit is \pm 3 days unless otherwise specified.
3. For women of reproductive potential, a urine or serum pregnancy test will be performed within 72 hours prior to first dose of trial treatment. If urine pregnancy results cannot be confirmed as negative, a serum pregnancy test, performed by the local study site laboratory, will be required. Pregnancy tests (serum and/or urine tests) should be repeated if required by local guidelines.
4. Coagulation factors (PT/INR and aPTT) should be monitored closely throughout the trial for any subject receiving anticoagulant therapy.
5. Laboratory tests for screening are to be performed within 10 days prior to the first dose of trial treatment.
6. After Cycle 1, lab samples can be collected up to 72 hours prior to the scheduled time point. Laboratory results must be known and acceptable prior to dosing.
7. The initial tumor imaging will be performed within 30 days prior to the first dose of trial treatment. Scans performed as part of routine clinical management are acceptable for use as the screening scan if they are of diagnostic quality and performed within 30 days prior to the first dose of trial treatment. On-study imaging will be performed every 6 weeks (42 -7 days) after the first dose of trial treatment or more frequently if clinically indicated. The timing for imaging studies should follow calendar days and should not be adjusted for delays in cycle starts or extension of MK-3475/afatinib cycle frequencies. The same imaging technique should be used in a subject throughout the trial. CT including the chest, abdomen and pelvis or PET-CT is required for the baseline assessment.
8. Provide documentation of the subject's tumor EGFR mutation from a CLIA certified laboratory.
9. MK-3475 can be administered for up to 2 years. For the dose de-escalation and Cohort (Arm) A (concurrent afatinib and MK-3475) both drugs will be administered as outlined in this protocol starting with cycle #1. For cohort B. MK-3475 will be initiated with cycle #1 and afatinib will commence in combination with MK-3475 starting with cycle #3.
10. Tumor biopsy for immune and EGFR biomarker analysis will be performed prior to Cycle 1 of treatment either on archival tissue or fresh biopsy (within 60 days). Repeat biopsy will be performed prior to initiation of cycle 3 (42 days (-7 days))

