7.1.2.6 Tumor Imaging and Assessment of Disease

For the purposes of this study, patients should be re-evaluated for response after cycle 2 (6 weeks) and then every 2 cycles (6 weeks). In addition to a baseline scan, confirmatory scans should also be obtained at least 4 weeks following initial documentation of objective response.

RECIST version 1.1* will be used in this study for assessment of tumor response. While either CT or MRI may be utilized, as per RECIST 1.1, CT is the preferred imaging technique in this study.

* As published in the European Journal of Cancer:

- PET-CT At present, the low dose or attenuation correction CT portion of a combined PET-CT is not always of optimal diagnostic CT quality for use with RECIST measurements. However, if the site can document that the CT performed as part of a PET-CT is of identical diagnostic quality to a diagnostic CT (with IV and oral contrast), then the CT portion of the PET-CT can be used for RECIST measurements and can be used interchangeably with conventional CT in accurately measuring cancer lesions over time. Note, however, that the PET portion of the CT introduces additional data which may bias an investigator if it is not routinely or serially performed.
- Conventional CT and MRI This guideline has defined measurability of lesions on CT scan based on the assumption that CT slice thickness is 5 mm or less. If CT scans have slice thickness greater than 5 mm, the minimum size for a measurable lesion should be twice the slice thickness. MRI is also acceptable in certain situations (e.g. for body scans).

Definitions

Evaluable for toxicity. All patients will be evaluable for toxicity from the time of their first treatment with *MK-3475 and afatinib*.

Evaluable for objective response. Only those patients who have measurable disease present at baseline, have received at least one cycle of therapy, and have had their disease re-evaluated will be considered evaluable for response. These patients will have their response classified according to the definitions stated below. (Note: Patients who exhibit objective disease progression prior to the end of cycle 1 will also be considered evaluable.)

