8.0 STATISTICAL ANALYSIS PLAN

8.1 Statistical Analysis Plan Summary

This is a phase I/Ib study. A minimum of 9 patients, if trial is terminated early due to unacceptable toxicity and a maximum of 38 patients (18 patients in the dose de-escalation cohort plus 10 in each of the two expansion cohorts) are anticipated for this trial. Analysis of safety and biomarkers will be limited to patients who receive active treatment.

The dose de-escalation phase will establish a MTD recommended dose of MK-3475 in combination with lead in MK-3475 followed by the combination or concurrent afatinib/MK-3475.

We plan to enter 3 patients at Dose Level 0. If 0/3 or 1/3 patients experience a DLT on level 0, an additional 3 patients will be accrued to Level 0, where 2 or more DLTs will terminate that study arm and we will proceed to dose level -1.

If 2 or more patients have DLTs at level 0, patients will be accrued at level -1. If 1/3 patients experience a DLT on level -1, an additional 3 patients will be accrued to Level -1, where 2 or more DLTs will require termination of that study arm while 1 DLT out of 6 will result in proceeding with dose level -1 as the MTD for the dose expansion cohorts.

If 2 or more patients have DLTs at level -1, patients will be accrued at level -2. If 1/3 patients experience a DLT on level -2, an additional 3 patients will be accrued to Level -2, where 2 or more DLTs will require termination of the study while 1 DLT out of 6 will result in proceeding with dose level -2 as the MTD for the dose expansion cohorts.

The phase I de-dose escalation portion of the trial will be closed when the maximum tolerated dose level (MTD) or dose level 0 is reached and six patients have been treated at that dose level.

Please see section 5.1.4.2 for further details.

All patients at a given dose level who have not experienced DLT, must be observed for a minimum of 21 days or until completion of their first cycle of therapy before the dose level can be escalated. Treatment will continue in an individual patient at the same dose level if no DLT is observed and if benefit is observed. There will be no dose escalation allowed for an individual patient.

The recommended phase II dose (RP2D) will be determined by the overall assessment of the MTD and toxicities observed in the de-dose escalation and dose expansion portion of this study.

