The baseline assumption is that single agent afatinib yields a response rate of 10% in this setting, and a response rate of 10% or less would not warrant further study. A response rate of 40% or greater would justify further study with a larger sample size. With 10 patients enrolled in cohort A expansion arm, we will declare this combination lacking promise if fewer than 3 patients respond, and potentially worthy of further study if 3 or more patients respond. If the true response rate is 10%, the chance of having 3 or more patients respond is 7%. If the true response rate is 40%, the

chance of having 3 or more patients respond is 83%.

If 3 or more patients respond, the response rate, toxicity, and progression-free survival will be evaluated to decide if larger randomized studies are warranted in this disease. Descriptive summaries will be provided for each of these summary measures (numbers and proportion responding, number and proportion with specific type and grade of toxicities, Kaplan-Meier plot and life-table summary of progression-free survival.) As stated earlier, a “pick the winner” approach between cohort A and cohort B based on toxicity: RR, PFS and changes in PDL1 expression will decide which dosing scheme to take further. It is assumed that a true RR >40% would be sufficient to recommend such development, provided safety and tolerability are also acceptable.

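### The only on-treatment adverse event window is tied to afatinib, so read literally it leaves out Cohort B's six-week MK-3475 lead-in, and the 28-day reporting sentence beside it contradicts the 30- and 90-day rules

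*Combined protocol and SAP*

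**What the plan says.** **On-treatment window.** Section 7.5: "Adverse events with onset within first administration of afatinib therapy and 28 days after last administration of afatinib will be considered as on treatment". Both ends are set by afatinib.

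**Cohort B schedule.** Section 6.1, footnote 9: "For cohort B. MK-3475 will be initiated with cycle #1 and afatinib will commence in combination with MK-3475 starting with cycle #3". Section 2.1 gives the lead-in as two cycles or six weeks, with 10 patients per cohort; section 5.1.4 sets the cycle at 21 days.

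**Safety analysis.** SAP 8.1: "Analysis of safety and biomarkers will be limited to patients who receive active treatment". It promises counts and proportions of toxicities by type and grade, and says that a pick-the-winner "approach between cohort A and cohort B based on toxicity: RR, PFS and changes in PDL1 expression will decide which dosing scheme" to develop. It states no adverse event window.

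**Toxicity evaluability.** Section 7.1.2.6: "All patients will be evaluable for toxicity from the time of their first treatment with" MK-3475 and afatinib. It does not say whether one drug is enough.

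**Reporting periods.**
- 7.5: all adverse events, from allocation to 30 days after treatment ends.
- 7.5, later in the same section: beyond 28 days after the last trial drug, serious and non-serious events alike are reported only if related to drug or trial procedure.
- 7.5.3.1 and 7.5.3.2: serious events and events of clinical interest (ECIs), related or not, to 90 days, or to 30 days if new anticancer therapy starts earlier.
- 7.5.3.1, reports to the afatinib supplier: the end of the period is an unfilled template prompt.

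**The concern.** The trial gives two study drugs, and one expansion cohort starts them six weeks apart. A window anchored to only one of them treats the two cohorts differently from day 1.

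Safety is the primary objective, and toxicity is one input to the choice between Cohorts A and B. If an analyst applies the protocol's only on-treatment label to the 8.1 tables, Cohort B alone loses its first two cycles. A Cohort B patient who never reaches afatinib contributes no on-treatment event, yet still belongs to the 8.1 safety population. Both effects at the start of the window favour the lead-in schedule.

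The reporting contradiction does not depend on how 8.1 is read. A site with an unrelated serious event on day 45 after the last dose finds one sentence that requires a report and another that rules it out.

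**Working it through.** **1. Lead-in length.** Inputs: 2 cycles (2.1), 21 days per cycle (5.1.4).
2 × 21 = 42 days = 6 weeks, which reproduces the figure in 2.1. The first afatinib dose falls on nominal day 43 in Cohort B (visit window ± 3 days) and on day 1 in Cohort A and in de-escalation.

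**2. Time outside the literal window at the start.**

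| Group | Days per patient | Total |
|---|---|---|
| Cohort B, 10 patients | 42 | 42 × 10 = 420 patient-days, or 2 × 10 = 20 patient-cycles, if all complete the lead-in |
| Cohort A and de-escalation | 0 | 0 |

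**3. Patients with no window.** The first response scan follows Cycle 2 (7.1.2.6), just before afatinib would start. Section 5.8 lists as a reason to discontinue: "Confirmed radiographic disease progression by RECIST 1.1". A Cohort B patient who stops at that point has received MK-3475 and so counts as treated under 8.1, but has no on-treatment period under 7.5.

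**4. End of the window.** Section 5.4 can allow one drug to continue while the other is held. Time on MK-3475 more than 28 days after a final afatinib dose is therefore also outside the window, in any cohort. The documents give no figure for how often this would happen.

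**5. Does another rule close the gap?**
- Dose-limiting toxicity uses its own clock: "The occurrence of any of the following toxicities during Cycle 1 will be considered a DLT", for either drug. It does not depend on the label.
- 8.1 defines a population (treated patients), not a window.
- 7.1.2.6 gives a start for evaluability but no end, and its wording can be read as needing both drugs.

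None of these settles which events enter the toxicity tables.

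**6. Contradictory reporting days.**

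| Event, unrelated to treatment | Required to | Ruled out after | Disputed days |
|---|---|---|---|
| Any adverse event | day 30 | day 28 | 30 − 28 = 2 (days 29–30) |
| Serious event or ECI | day 90 | day 28 | 90 − 28 = 62 (days 29–90); 62/90 = 69% |
| Serious event or ECI, new therapy started | day 30 | day 28 | 30 − 28 = 2 |

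The 30-day all-event rule and the 90-day serious-event and ECI rules can coexist. The 28-day sentence is compatible with neither. The open-ended rule in 7.5.3.1 does not help, because it covers only serious events related to MK-3475.

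**7. Illustration of what could be missed.** The documents give no per-cycle risk, so the following rests on an assumption. If each Cohort B patient has probability q of a given event during the lead-in, the chance that at least one of 10 has it is 1 − (1 − q)^10: 40% for q = 5%, 65% for q = 10%, 89% for q = 20%. This shows only that lead-in events are likely to exist at plausible rates. It is not an estimate of bias.

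**The case against.** **8.1 never uses the label.** The natural default is that every collected event in a treated patient is tabulated. Lead-in events are collected from allocation, with onset dates, so any misclassification can be undone at analysis. This stands as a limit: the bias is conditional, and the fault is one of classification, not lost data. It does not remove the need to state the window, because 8.1 gives none and the only available definition is wrong for Cohort B.

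**The direction is not certain.** Losses at the end of the window can occur in Cohort A too. This also stands: the start-of-treatment effect favours Cohort B, but the net direction cannot be derived from the documents.

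**A scan showing progression need not end treatment.** Section 5.8 allows an exception for patients who are clinically stable or improved. That makes stopping before Cycle 3 less certain, but still foreseeable.

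**Sites would follow the dedicated 90-day rules.** Section 7.5 points elsewhere for the timing of serious events. But it points to section 7.5, which contains both rules. The 28-day sentence names serious events explicitly, names no recipient and refers to the trial drugs generally. Reading it as a rule for the afatinib supplier alone would be an inference.

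**The choice affected is descriptive, between two small sequential cohorts.** This is true, and it limits the severity.

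**Conclusion.** The concern holds. As written, the only on-treatment definition excludes 42 days of study treatment per Cohort B patient (up to 420 patient-days) and none at the start in Cohort A, and it leaves a Cohort B patient who never starts afatinib without a window. Whether this distorts the comparison of cohorts depends on whether the label is applied to the 8.1 summaries, which the plan does not say. The effect on toxicity rates cannot be calculated from the documents.

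The reporting contradiction is unconditional: 2 days for unrelated events in general, and 62 of 90 days for unrelated serious events and ECIs (2 days once new anticancer therapy starts).

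This should be fixed before the toxicity tables are produced. It does not affect dose-limiting toxicity assessment or the response rule.

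**What to change.** - **7.5:** open the on-treatment window at the first dose of either study drug and close it a stated number of days after the last dose of either. That number should equal the single all-event collection period kept after reconciliation (28 or 30 days, the two now in 7.5).
- **7.1.2.6:** start toxicity evaluability at the first dose of either drug.
- **8.1:** state that the toxicity summaries use this window. Report later related events, and later serious events and ECIs to 90 days, separately so that they are not dropped. Preferably tabulate Cohort B toxicity for Cycles 1–2, for Cycle 3 onward and for both together, with the number of patients who started each period.
- **Reporting rules:** reconcile the 28-day sentence with the 30-day all-event rule and the 90-day rules in 7.5.3.1 and 7.5.3.2. Align 1.0 Trial Summary, whose 30-day line covers only drug-related events, and 7.4.3.1, which gives 30 days for serious events. Fill in the blank period for reports to the afatinib supplier.

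**Cost:** wording changes and one table split. No new data are needed: onset dates and all events to 30 days are already collected, and serious events and ECIs to 90 days are already required. No sample size or error rate changes.
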